#### Baseline Assessments

Baseline assessments listed below must be completed post-enrollment and within 24 hours prior to the first dose of study therapy unless otherwise specified.

- 1. Karnofsky or Lansky Performance Status (may be completed pre- or post-enrollment)
- 2. Baseline patient-reported outcome measures (Appendix F)
- 3. Peripheral blood for EBV and CMV viral load (within 72 hours prior to first T-Guard dose)
- 4. Peripheral blood\* for EBV, CMV-specific and alloreactive T-cells (See Appendix B)
- 5. CBC with differential and platelet count\* (must be collected at the same time as the 30mL peripheral blood for alloreactive T-cells)
- Peripheral blood\* for humoral response (ADA) and immunophenotyping (See Appendix B)
- 7. Peripheral blood\* and urine sample\* for GVHD biomarker testing (See Appendix B)
- 8. Recording of all systemic immune suppressive therapy (as appropriate: tacrolimus, cyclosporine, etc.), as well as topical agents
- 9. History and physical exam including height and weight, patient disease/transplantation baseline variables (may be completed pre- or post-enrollment but must be within 7 days prior to first T-Guard dose)

#### At Each Infusion of T-Guard Therapy

- 1. Complete acute GVHD staging and grading information including assessments of rash, diarrhea, nausea/vomiting, and bilirubin
- 2. Vital signs (temperature, pulse, respiratory rate, blood pressure) just before starting the infusion, 15 minutes after the start of the infusion, 30 minutes after the start of the infusion, then every 30 minutes during the infusion, and at 1-hour post-infusion\*. Deviation of +/- 5 minutes may occur for all vital sign collection timepoints.
- 3. Albumin and platelet count prior to each dose of T-Guard
- 4. CBC with differential
- Peripheral blood\* for immunophenotyping studies pre-infusion and at 4 hours after the start of infusion. Pre-infusion samples should be drawn prior to T-Guard administration and a window of +/- 15 minutes is allowed for the sample drawn 4 hours after the start of infusion.
- 6. Peripheral blood\* for PK at the following timepoints
  - a. 1st infusion: pre-infusion, and at 4, 5, 6, 8, and 24 hours after start of infusion
  - b. 2nd infusion: pre-infusion, and at 4, 6, and 24 hours after start of infusion
  - c. 3rd infusion: pre-infusion, and at 4, 6, and 24 hours after start of infusion
  - d. 4th infusion: pre-infusion, and at 4, 6, 24, and 48 hours after start of infusion

Pre-infusion samples should be drawn prior to T-Guard administration. A window of +/- 15 minutes for samples drawn at 4,5, or 6 hours after the start of infusion, and a window of +/-30

minutes for the sample drawn 8 hours after the start of infusion is allowed. A window of +/- 2 hours for samples drawn 24 or 48 hours after the start of infusion is also allowed. Every effort should be made to collect PK samples at all timepoints, however, the treatment schedule should not be altered to accommodate PK sampling. For example, if T-Guard administration is scheduled for a weekend and PK sampling is not possible then administration should occur on schedule. In the event weekend PK sample collection is missed, collection of PK samples should be resumed at the next T-Guard infusion. Please refer to Section 4.5 for more information regarding infusion delays.

#### Post-Initiation of T-Guard Therapy

The following assessments and observations must be completed at the timepoints designated below.

- 1. Complete acute GVHD staging and grading information including assessments of rash, diarrhea, nausea/vomiting, and bilirubin at Days 7, 14, 21, 28, 35, 42, 49, 56, 70, 90, and 180
- 2. Albumin and platelet count at Days 28, 56, 90, and 180
- 3. CBC with differential at Days 28, 56, 90, and 180 (must be collected at the same time as the 30mL peripheral blood for alloreactive T-cell sample on Days 28 and 180)
- 4. Karnofsky or Lansky performance status at Days 28, 56, 90, and 180
- Peripheral blood for EBV and CMV viral load at Days 28 and 180 with monitoring of EBV and CMV continuing per institutional practice post Day 28 through 180 days post initiation of T-Guard
- 6. Peripheral blood\* for EBV, CMV-specific and alloreactive T-cells at Days 28 and 180
- 7. Patient reported outcomes at Days 28, 56 and 180 post initiation of T-Guard
- 8. cGVHD evaluation (if present) Day 28, 56, 90, and 180
- 9. Peripheral blood\* for ADA testing at Days 7, 14, 28, 90, and 180
- 10. Peripheral blood\* for immunophenotyping studies at Days 14, 28, 56, and 180
- 11. Peripheral blood\* and urine sample\* at Days 7, 14, and 28 for GVHD biomarker testing
- 12. Recording of all systemic immune suppressive therapy (as appropriate: tacrolimus, cyclosporine, etc.), as well as topical agents, and all anti-infectives used for prophylaxis or treatment at Days 7, 14, 21, 28, 35, 42, 49, 56, 70, 90, and 180
- 13. Recording of toxicities on Days 56, 70, 90, and 180
- 14. Recording of AE/SAEs as described in Section 4.4 Adverse Event Reporting
- 15. Recording of infections through Day 180
- 16. Recording of primary disease relapse through Day 180

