#### 1.3.2.4 Safety

The most common side-effects described for RTA-based immunotoxins are vascular leakage and myalgia, the latter being often associated with an increase in serum creatine kinase (CK). Moreover, the systemic administration of anti-CD3 antibodies may result in the activation of Tcells leading to CRS. In both trials T-Guard was overall well-tolerated. Mild infusion related reactions, such as mild chills, were documented. However, no acute toxicity reactions seen were greater than Grade 1. The most commonly reported AEs considered to be related to T- Guard administration were hypoalbuminemia and thrombocytopenia.

The potentially drug-associated side effects occurring in more than one patient consisted of (further) decrease in platelet count (thrombocytopenia), hypoalbuminemia and thrombotic microangiopathy. Regarding thrombocytopenia and hypoalbuminemia, the patients in the study already had a low platelet count and albumin level due to aGVHD and medication. Nevertheless, in several patients, a further decrease was observed during the treatment period. According to the Principal Investigators, thrombocytopenia and hypoalbuminemia were well-manageable. TEAEs from the overall study are outlined in Table 1-1 from the Phase I/II Trial.

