# Table 1-2: Summary of Adverse Events Potentially Related to Treatment (Groth, van Groningen et al. 2018)

Grade 2ª	Grade 3	Grade 4
Anemia (1) b	Thrombocytopenia (3)	Thrombocytopenia (5)
Abdominal pain (1)	Neutropenia (1)	
Thrombocytopenia (1)	Elevated bilirubin (2)	
Neutropenia (1)	Myopathy (1)	
Microangiopathy (1)	Microangiopathy (1)	

Grade 2ª	Grade 3	Grade 4
Chills (2)	Hypoalbuminemia (1)	
Capillary leak syndrome (1)		
Hypoalbuminemia (1)		

Grading of each AE is based on version 4.0 of the CTCAE, with the exception of CLS, which was graded using the system described by Messmann et al. (Messmann, Vitetta et al. 2000)

The numbers in parentheses refer to the number of patients who experienced the indicated adverse event.

The overall conclusion of the Phase 1/2 study is that T-Guard was well tolerated and can be safely administered in patients with SR-aGVHD. Additionally, the response rates, in particular CR rates, at Day 28 were markedly superior (CR 50%) to historical controls and the results of emerging therapies (CR 20-35%).

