# 2.5.4 Dose and Administration of T-Guard

T-Guard will be administered at a dose of 4mg/m^2 (actual body weight) over 4 hours every 2 calendar days on Days 0, 2, 4, and 6. Infusions of T-Guard that exceed 4 hours are not considered deviations. Pauses in the infusion due to a patient reaction need to be documented.

The maximum BSA to be used in dose calculation is 2.5 m^2. If the patient's BSA is more than

2.5 m^2, the dose calculation should use 2.5 m^2. The patient's weight on the day of the first dose will determine the dose for the remaining infusions (dose adjustments for changes in weight during the treatment period will not be made).

Premedication with diphenhydramine 50 mg by mouth or 25 mg IV should be administered 30 minutes prior to each dose. For pediatric patients, the diphenhydramine dose should not exceed 1 mg/kg. Premedication with acetaminophen is permitted.

It is recommended that T-Guard be infused via a central catheter using a dedicated line or can be administered via a peripheral line, if needed. If a multi-lumen central venous catheter is used, T-Guard and crystalloid or total parenteral nutrition should be administered through different lumens of the catheter. PK samples should be drawn from the central catheter using a different lumen than the lumen used for infusion.

Before the infusion, connect the syringe with the in-line filter and luer-lock extension tube to a central venous catheter (recommended) or peripheral line. The contents of the syringe will then be administered by means of an automated infusion device, over a period of 4 hours. Once the infusion syringe is empty, the administration tubes will be flushed.

Vital signs (temperature, pulse, respiratory rate, blood pressure), should be checked at the following timepoints with each infusion: just before starting the infusion, 15 minutes after the start of the infusion, 30 minutes after the start of the infusion, then every 30 minutes during the infusion, and at 1-hour post-infusion. Deviation of +/- 5 minutes may occur for all vital sign collection timepoints.

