#### Myalgia and serum CK-elevation:

There is an association of myositis with Ricin-based immunotoxicity. Therefore, patients should be monitored for signs of myositis. If patients experience muscle pain, then a serum CK should be performed. The next dosage of T-Guard should be withheld in case of a CK elevation greater than 5 times ULN. Dosing can resume if the CK decreases to less than or equal to 5 ULN and symptoms of myositis has improved to Grade 2 or less by CTCAE v.5. Dosing can proceed at the investigator's discretion if deemed in the best interest of the patient.

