# 2.5.6 T-Guard Discontinuation

T-Guard treatment must be completed within 14 days of the first study drug dose. Patients who have missed doses may re-start T-Guard provided it is within the 14-day treatment window.

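### No albumin, platelet or CBC value is required for 22 days after the planned last infusion, and the CK passages do not say which patients the 5 x ULN limit covers

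*Combined protocol and SAP*

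**What the plan says.** Section 4.3.2 sets the laboratory schedule in blocks, and Table 4.2 shows the same gap at Days 7, 14 and 21.

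- **Before enrollment:** albumin, platelets, CK and CBC, all within 24 hours.
- **At each infusion:** "Albumin and platelet count prior to each dose of T-Guard", and a CBC. Section 2.5.4 plans infusions "every 2 calendar days on Days 0, 2, 4, and 6".
- **After treatment starts:** "Albumin and platelet count at Days 28, 56, 90, and 180" (item 2) and "CBC with differential at Days 28, 56, 90, and 180" (item 3).

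Visits do take place on Days 7, 14 and 21. Each includes acute GVHD staging with bilirubin, and Days 7 and 14 also include blood for ADA and biomarkers.

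In section 1.3.2.4, the sentence on the most commonly reported related events ends "Guard administration were hypoalbuminemia and thrombocytopenia". The toxicity endpoint (sections 3.4.2.9 and 5.4.11) covers Grade 3-5 events from the first infusion to 28 days after the last.

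For CK, exclusion criterion 5 in section 2.4.2 applies a limit of 5 x ULN to every patient. Section 2.5.5 withholds the next dose when CK is above the same limit and asks sites to watch for signs of myositis. The only instruction to measure CK after enrollment is "If patients experience muscle pain, then a serum CK should be performed", repeated in footnote 2 of Table 4.2.

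**The concern.** The gap falls on the two laboratory toxicities that the protocol itself puts first. A sample drawn before an infusion can reflect only the earlier doses, so no required albumin or platelet value reflects the fourth dose until Day 28.

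Serial values matter here for two reasons. Section 1.3.2.4 says patients already had low platelets and albumin from GVHD and medication, and that the signal in several of them was a further fall. The trial also has no control arm, so change within a patient is the main evidence on what the drug does to these values. If the post-dose values come only from tests that each center chose to run, the reported frequency and depth of the fall partly reflect local practice.

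The CK question is different. One threshold appears in two places without a symptom condition, while the only stated reason to test is a symptom. The documents do not say whether that is intended.

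**Working it through.** No power or error-rate figure bears on this point, and the plan states no figure to reproduce. The check is a comparison of schedules and subtraction of days. Days are counted from the first infusion, as section 4.3.1 states.

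**Step 1. Gap with on-time dosing.** The last required sample precedes the Day 6 infusion and the next is Day 28: 28 - 6 = 22 days. Table 4.1 allows 3 days either side of Day 28, so 25 - 6 = 19 to 31 - 6 = 25 days.

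**Step 2. Gap with delayed dosing.** Section 2.5.6: "T-Guard treatment must be completed within 14 days of the first study drug dose". Section 4.5 moves albumin and platelets with a delayed infusion. If the last dose is on Day 14, the gap is 28 - 14 = 14 days, with a range of 25 - 14 = 11 to 31 - 14 = 17.

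**Step 3. Share of the toxicity window after the last dose.**

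| Last dose | Window closes | Days before the next required value | Share of 28 days |
|---|---|---|---|
| Day 6 | 6 + 28 = Day 34 | 22 | 22/28 = 79% |
| Day 14 | 14 + 28 = Day 42 | 14 | 14/28 = 50% |

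In both cases the Day 28 sample lies inside the window.

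**Step 4. Does other reporting fill the gap?**
- Section 4.4.4 requires all adverse events to be reported through 30 days after the last dose, and Table 4.2 marks AE assessment at Days 7, 14, 21 and 28.
- Section 4.4.1 counts an abnormal test as an adverse event only if it causes signs or symptoms, needs active intervention, interrupts or stops study drug, or is clinically significant in the investigator's opinion. After the fourth dose there is no drug left to interrupt, so three conditions remain. All of them presuppose that someone took a sample.
- Calendar toxicity recording (section 4.3.2, post-initiation item 13) starts on Day 56, after the window closes on Day 34 or, at the latest, Day 42.

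**Step 5. Size of the earlier signal.** Table 1-2 lists potentially related thrombocytopenia at Grade 4 in 5 patients: 5/20 = 25%. A further 3 are listed at Grade 3. The total would be 8/20 = 40% only if the two cells hold different patients. Table 1-1 lists the term thrombocytopenia in 6 of 20, so overlap or different coding is possible, and I rely only on the 5. Hypoalbuminemia of any cause is 8/20 = 40% in Table 1-1. Potentially related entries in Table 1-2 are one at Grade 2 and one at Grade 3.

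**Step 6. CK passages side by side.**

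| Place | Who is covered |
|---|---|
| 2.4.2, exclusion 5 | every patient, with or without symptoms |
| 4.3.2, Prior to Enrollment, item 2 | every patient, once |
| 2.5.5, hold rule | any CK above 5 x ULN |
| 2.5.5 and Table 4.2 footnote 2, when to test | patients with muscle pain |

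Required CK values after enrollment in a patient without muscle pain: 0. Table 1-1 records muscular weakness and myopathy in 5/20 each. Neither term is named as a reason to test, although section 2.5.5 asks for monitoring of signs of myositis.

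**The case against.** The strongest reply is that not required does not mean not done. Section 4.3.2 classes these laboratory tests as standard of care, adverse events are assessed weekly through Day 28 and beyond, and albumin is required before every dose, which is when it informs dosing. After the fourth dose no dosing decision remains. The toxicity endpoint is a descriptive table, and the primary endpoint and its boundaries are unaffected.

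Most of this stands, and it limits the point to completeness of safety data. It does not remove the point, because standard-of-care testing does not ensure that the same values are recorded at the same times in every patient. More values would not automatically become adverse events under section 4.4.1, but they would give a uniform series to tabulate.

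Three stronger readings are tempting and are not supported:

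- A reader might infer that these toxicities are never measured after the last dose. Albumin and platelets are required at Days 28, 56, 90 and 180, and Day 28 is inside the toxicity window.
- A reader might infer that monitoring of capillary leak syndrome (CLS) is impaired, since section 2.5.5 calls severe hypoalbuminemia a risk for it. The monitored event in section 5.2.2 is Grade 4 or higher CLS. Section 2.5.5 describes severe CLS by pressors, dialysis or ventilation, none of which needs a scheduled albumin. The Phase 1/2 cases were 7 mild and 1 moderate (section 1.3.3).
- A reader might infer that the CK hold rule covers only patients with pain. Its text covers any CK above the limit; only the stated trigger for testing is narrower. Sections 1.3.2.4 and 1.2.1 also give context: myalgia is the symptom often associated with raised CK, and myopathy is a known steroid toxicity. The all-cause muscle counts are therefore weak evidence of a drug effect.

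**Conclusion.** The schedule gap is real and worth closing because closing it is cheap. With on-time dosing there is no protocol-required albumin, platelet or CBC value for 22 days after the last infusion, which is 79% of the post-dose toxicity window. The gap is 14 days, or 50%, if dosing ends on Day 14. The consequence is non-uniform collection of rates and nadirs for the two most commonly reported related toxicities. The documents do not show how often centers would test anyway, so the number of missed abnormalities cannot be estimated. No claim is made here about how CTCAE grades these values, because its criteria for them are not reproduced in the documents.

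On CK, the passages leave the intended coverage of the 5 x ULN limit unstated. That calls for reconciliation. Nothing here says which reading is clinically right.

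**What to change.** In section 4.3.2 (post-initiation item 2) and Table 4.2, add collection of platelet count and albumin at the existing Day 7, 14 and 21 visits. With the last dose on Day 6, required values would then fall at planned intervals of 1, 8, 15 and 22 days after it. If a delayed infusion coincides with the Day 7 or Day 14 visit, section 4.5 already combines the assessments, so no duplicate sample is needed. In that case the first post-dose value comes from the next weekly visit. The cost is a few more laboratory values to record at visits where bilirubin is already required.

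For CK, the sponsor should reconcile section 2.4.2 (exclusion 5), section 2.5.5, the pre-enrollment list in section 4.3.2 and footnote 2 of Table 4.2, and state which patients the threshold is meant to cover. No CK schedule or hold rule is proposed.

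While editing, the sponsor should also reconcile the Day 56 start of calendar toxicity recording with the endpoint window in section 3.4.2.9 and the reporting rules in section 4.4.4, and name the data source for toxicities inside that window. This is a wording change only.

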#### Table 4.2: Assessment Schedule

	Pre- Enrollment	Baseline 		of T- fusio		ard				C	ays	Post	Initia	tion c	of T-G	luard	
	Base	line	0	2	4	6	7	14	21	28	35	42	49	56	70	90	180
Acute GVHD evaluation, including bilirubin	х		х	х	х	х	х	х	х	х	х	х	х	х	х	х	Х
Chronic GVHD evaluation										Х				Х		Х	Х
Recording of all systemic immune suppression, including steroid dose		х					х	x	x	x	х	x	x	x	x	х	х
History and physical exam		Х															
CBC with differential		X 	Х	Х						X 				Х		Х	X 
Platelet count	Х	X 	Х	Х		Х				X 				Х		Х	X 
Albumin	Х		Х	Х	Х	Х				Х				Х		Х	Х
CK levels 	Х																
Pregnancy test (if applicable)	Х																
Karnofsky/Lansky performance status		х								х				х		х	х
	Pre- Enrollment	Baseline 		of T- fusio		ard				D	)ays	Post	Initia	tion c	of T-G	luard	
	Base	line	0	2	4	6	7	14	21	28	35	42	49	56	70	90	180
Peripheral blood for CMV and EBV viral load		х								х							х
Peripheral blood for EBV, CMV-specific and alloreactive T- cells 		x								х							х
Pharmacokinetics 			Х	Х	Х	Х											
Peripheral blood for ADA		Х					Х	Х		Х						Х	Х
Peripheral blood for GVHD biomarkers REG3α and ST2		х					Х	х		х							
Peripheral blood for immunophenotyping 		х	х	x	х	х		x		х				х			х
Urine sample for GVHD biomarker 3-IS		х					Х	х		х							
Vital signs (temperature, pulse, respiratory rate, blood pressure) 			х	x	х	x											
AE/SAE assessment 			x	x	x	х	х	x	x	х	х	х	х	x	х	х	х
Toxicity assessment														x	x	х	х
Patient-reported outcomes: PROMIS		х								х				х			Х
Infection monitoring	Re	eporting of	infectio	ons a	at tir	ne d	of occ	urre	nce	from	n time	e of e	nrollr	nent	throu	gh Da	y 180
Primary disease relapse reporting		Reporting c														-	-

Baseline assessments must be completed post enrollment and within 24 hours prior to the first dose of study treatment unless otherwise specified.

If patients experience muscle pain, then a serum CK should be performed.

The CBC with differential and platelet count must be taken at the same time as the peripheral blood is drawn for EBV, CMV-specific and alloreactive T-cells at baseline, day 28, and day 180.

Pharmcokinetic blood samples directly pre-infusion, and at 4, 5, 6, 8, and 24 hours after start of 1st infusion, preinfusion, and at 4, 6, and 24 hours after the 2nd and 3rd infusion, and pre-infusion, and at 4, 6, 24 and 48 hours after the 4th T-Guard infusion.

Pre-infusion samples should be drawn prior to T-Guard administration. A window of +/- 15 minutes for samples drawn at 4,5, or 6 hours after the start of infusion, and a window of +/-30 minutes for the sample drawn 8 hours after the start of infusion is allowed. A window of +/- 2 hours for samples drawn 24 or 48 hours after the start of infusion is also allowed. Every effort should be made to collect PK samples at all timepoints, however, the treatment schedule should not be altered to accommodate PK sampling. For example, if T-Guard administration is scheduled for a weekend and PK

sampling is not possible then administration should occur on schedule. In the event weekend PK sample collection is missed, collection of PK samples should be resumed at the next T- Guard infusion.

Peripheral blood for immunophenotyping should be collected pre-infusion and at 4 hours after the start of each infusion. Preinfusion samples should be drawn prior to T-Guard administration and a window of +/- 15 minutes is allowed for the sample drawn 4 hours after the start of infusion.

Vital signs should be taken directly pre-infusion, 15 minutes after the start of the infusion, 30 minutes after the start of the infusion, then every 30 minutes during the infusion, and at 1-hour post-infusion. Deviation of +/- 5 minutes may occur for all vital sign collection timepoints.

 AEs and SAEs will be reported as described in Section 4.4 Adverse Event Reporting

# 4.4 ADVERSE EVENT REPORTING

AE reporting requirements are summarized below.

# 4.4.1 Definitions

Adverse Event: An AE is any untoward medical occurrence in a patient administered an investigational product or has undergone study procedures and which does not necessarily have a causal relationship with this treatment. An AE can therefore be any unfavorable and unintended sign (including an abnormal laboratory finding), symptom, or disease that is temporally associated with the use of a medicinal (investigational) product, whether or not related to the medicinal (investigational) product.

An abnormality identified during a medical test (e.g., laboratory parameter, vital sign, ECG data, physical exam) should be defined as an AE only if the abnormality meets 1 of the following criteria:

- Induces clinical signs or symptoms.
- Requires active intervention.
- Requires interruption or discontinuation of study medication.
- The abnormality or investigational value is clinically significant in the opinion of the investigator.

**Serious Adverse Event:** An SAE, as defined by per 21 CFR 312.32, is any adverse event that results in one of the following outcomes, regardless of causality and expectedness:

- Results in death
- Is life-threatening. Life-threatening means that the person was at immediate risk of death from the reaction as it occurred, i.e., it does not include a reaction which hypothetically might have caused death had it occurred in a more severe form.
- Requires or prolongs inpatient hospitalization (i.e., the event required at least a 24hour hospitalization or prolonged a hospitalization beyond the expected length of stay). Hospitalization admissions and/or surgical operations scheduled to occur during the study period but planned prior to study entry are not considered SAEs if the illness or disease existed before the person was enrolled in the trial, provided that it did not deteriorate in an unexpected manner during the trial (e.g., surgery performed earlier than planned).
- **Results in persistent or significant disability/incapacity**. Disability is defined as a substantial disruption of a person's ability to conduct normal life functions.
- Is a congenital anomaly or birth defect; or
- Is an important medical event when, based upon appropriate medical judgment, it may jeopardize the patient and require medical or surgical intervention to prevent one of the outcomes listed above. Examples of such medical events include allergic bronchospasm requiring intensive treatment in an emergency room or at home; blood dyscrasias or convulsions that do not result in inpatient hospitalization, or the development of drug dependency or drug abuse.

Medical and scientific judgment should be exercised in deciding whether expected reporting is also appropriate in situations other than those listed above. For example, important medical events may not be immediately life threatening or result in death or hospitalization but may

jeopardize the patient or may require intervention to prevent one of the outcomes listed in the definition above (e.g., suspected transmission of an infectious agent by a medicinal product is considered an SAE). Any event is considered a SAE if it is associated with clinical signs or symptoms judged by the investigator to have a significant clinical impact.

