# 3.4.2.9 Incidence of Toxicities

All grade 3-5 toxicities according to CTCAE v5 occurring from the initiation of T-Guard treatment to 28 days post last dose will be described.

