# 4.4.4 Required Adverse Event Reporting

Any unanticipated SAEs from time of enrollment through the study defined follow up are required to be reported following the BMT CTN Administrative MOP Chapter 6. Additionally, any grade 4 anticipated event not collected on the calendar-driven toxicity or specified event- driven form must **also** be reported through the expedited AE reporting system in Advantage eClinical. Chapter 6 of the BMT CTN MOP defines reporting based on the terms Unexpected and Expected; however, for this study, the reporting will be based on the terms Unanticipated and Anticipated All adverse events, including SAEs, must be reported from the 1st dose of T- Guard through 30 days after the last dose. In addition, any SAEs occurring after that 30-day period, but assessed as related to the investigational product, must be reported. All SAEs are to be followed up until resolved, judged to be no longer clinically significant, or until they become chronic to the extent that they can be fully characterized.

Infections are collected separately in eClinical as this is a study endpoint; however, should an infection meet the SAE criteria the infection must also be reported following the SAE reporting criteria outlined above.

GVHD and underlying disease relapse events are also collected separately in eClinical because they are part of the endpoint analysis. Events of GVHD and underlying disease relapse are not to be reported as AEs/SAEs for this study.

The Sponsor has a list of events classified as Special Situations. These events are 1) medication error, 2) overdose and 3) pregnancy. These events must be reported following the reporting for SAEs.

SAEs that require reporting will be reported through an expedited AE reporting system via an EDC. All SAEs, as well as Special Situations, must be reported within 24 hours of knowledge of the event. Events entered in EDC will be reported using NCI's CTCAE Version 5.0. If there are network outages, a paper copy of the AE form must be completed and emailed to Emmes to initiate Sponsor review. Once the system is available, the event information must be entered into the system.

Anticipated AEs will be reported using NCI's CTCAE Version 5.0 at regular intervals as defined on the Form Submission Schedule, including calendar-driven eCRFs (e.g., Toxicity and GVHD) or event-driven eCRFs (e.g., Relapse/Progression, Infection, Secondary Graft Failure and Death).

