#### 5.4.11 Incidence of Toxicities

The frequency of Grade 3-5 toxicities per CTCAE version 5 occurring from the initiation of T-Guard treatment until 28 days post-last dose will be tabulated by organ system. The maximum severity of reported toxicities during that period will also be summarized.

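### The Grade 3-5 toxicity table can omit Grade 3-4 laboratory values, because the only event capture scheduled in its window is AE reporting, which has no grade threshold

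*Combined protocol and SAP*

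**What the plan says.** The endpoint in section 3.4.2.9 is worded without exception: "All grade 3-5 toxicities according to CTCAE v5 occurring from the initiation of T-Guard treatment to 28 days post last dose will be described". Section 5.4.11 tabulates "The frequency of Grade 3-5 toxicities per CTCAE version 5" over the same period by organ system, with maximum severity. Neither section names the form or dataset that feeds the table, and neither refers to the AE definition.

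Section 4.4.4 sets the reporting duty: "All adverse events, including SAEs, must be reported from the 1st dose", continuing to 30 days after the last dose. Section 4.4.1 defines what is reportable. An abnormality found on a medical test "should be defined as an AE only if the abnormality meets 1 of the following criteria". The four criteria are that it induces signs or symptoms; "Requires active intervention"; "Requires interruption or discontinuation of study medication"; or "The abnormality or investigational value is clinically significant in the opinion of the investigator".

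Section 4.3.2 and Table 4.2 schedule AE/SAE assessment at every visit from Day 0, but toxicity recording only at Days 56, 70, 90 and 180.

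**The concern.** The endpoint is defined by CTCAE grade, whereas the data arriving in its window are selected by criteria that do not mention grade. An asymptomatic Grade 3 platelet, neutrophil or albumin value that is observed without treatment, does not interrupt dosing and is not judged clinically significant belongs in the endpoint as worded, yet has no scheduled route into it.

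The trial has a single arm of 47 treated patients, so the toxicity table is an absolute frequency. There is no control arm in which the same under-recording would occur, and any omission lowers the reported figure directly. The population makes omission plausible. Section 1.3.2.4 says of Phase I/II that "the patients in the study already had a low platelet count and albumin level due to aGVHD and medication", and that the investigators found further falls manageable. A value seen as usual for the population is one that may be judged not clinically significant.

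**Working it through.** The plan gives no expected Grade 3-5 rate and no AE capture fraction, so there is no figure to reproduce. The check compares windows, schedule and criteria, and then counts Table 1-2.

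**1. Endpoint window.** The last dose is planned for Day 6 (section 2.5.4) and must fall within 14 days of the first (section 2.5.6).
- Endpoint closes: 6 + 28 = Day 34; at the latest 14 + 28 = Day 42.
- AE reporting closes: 6 + 30 = Day 36; at the latest 14 + 30 = Day 44.
- First toxicity form: Day 56, which is 56 − 34 = 22 or 56 − 42 = 14 days after the endpoint window has closed.

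No toxicity form falls inside the window. The AE/SAE assessment does, at every visit.

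**2. The four criteria.** They are alternatives.
- Signs or symptoms: an asymptomatic value does not qualify.
- Active intervention: a transfusion would plausibly qualify (section 2.5.8.4 lists transfusion support). Observation would not.
- Interruption of study drug: section 2.5.5 has hold rules for albumin and CK, and its general rule covers non-hematologic toxicity. It names no hold for platelets or neutrophils. This route also ends with the last dose, while the window runs 28 days longer.
- Clinical significance: the investigator's opinion, with no grade threshold.

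A Grade 3-4 value can therefore fail all four.

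**3. Possible safeguards in section 4.4.4.**
- The calendar-driven Toxicity form collects anticipated AEs. It starts at Day 56, and neither its look-back nor its items are given.
- Grade 4 anticipated events not collected on a form must be reported through the expedited system. This does nothing for Grade 3, and section 4.4.1 defines anticipated events as a kind of adverse event.

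**4. Size of the category.** Table 1-2 gives patients per event and grade.
- Grade 3: thrombocytopenia 3, neutropenia 1, elevated bilirubin 2, myopathy 1, microangiopathy 1, hypoalbuminemia 1; total 9.
- Grade 4: thrombocytopenia 5. Total 9 + 5 = 14.
- Laboratory-defined: 3 + 1 + 2 + 1 + 5 = 12, and 12/14 = 86%.
- Platelets and neutrophils alone: 3 + 5 + 1 = 9 of 14.

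**5. Share lost.** Let q be the fraction of laboratory Grade 3-4 events meeting none of the criteria. On the Table 1-2 mix the loss is q × 12/14. With q purely assumed, 10% gives 1.2/14 = 8.6% and 75% gives 9/14 = 64%. Nothing in the documents narrows q, so this range is not an estimate.

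**6. Values available for direct grading.** Section 4.3.2 requires albumin and platelets before each dose, a CBC with differential at each infusion, and all of these again at Day 28. For albumin and platelets the sample before the first dose is a starting value, which leaves four scheduled later draws: before infusions 2, 3 and 4, and Day 28. Bilirubin is part of every aGVHD assessment, at each infusion and weekly from Day 7 to Day 56. After enrollment, CK is required only for muscle pain.

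**The case against.** The strongest reply is that the link between the AE filter and the endpoint is inferred. The endpoint speaks of toxicities, not AEs. A separate Toxicity form exists, and its detail sits in the Form Submission Schedule, the Data Management Handbook and the eCRF guide, which are not part of these documents. The Day 56 form could look back over the window. That is possible, but the protocol does not say so, and section 4.4.4 describes the form as collecting anticipated AEs, so a look-back alone need not remove the filter.

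The criteria are also broader than investigator opinion. Three of the four are not expressly opinion, and treatment of any kind qualifies. This stands, and it is why a reader who infers that most laboratory-defined toxicity would be lost goes beyond the documents: that needs q above 50%, which nothing supports.

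A reader might also infer that a value attributed to aGVHD stops being an AE. Section 4.4.1 says the opposite: an AE need not be related to the product, and events resulting from the underlying disease, the transplant or aGVHD are classed as anticipated adverse events. GVHD itself is kept out of AE reporting by section 4.4.4, because it is collected separately.

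Table 1-2 should not be scaled to 47 patients. It lists only potentially related events, while the endpoint takes all; one patient may appear in several entries; and the AE definition used in that study is not given. The table also shows that laboratory Grade 3-4 events were reported there. Open-label conduct adds little: with one arm there is no differential reporting, only possible under-reporting.

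Finally, counting raw values has its own fault. It would count low starting values as toxicity, and bilirubin is the liver staging variable in Appendix C. This objection is sound and shapes the fix.

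**Conclusion.** The mismatch stands. Sections 3.4.2.9 and 5.4.11 define the endpoint by CTCAE grade, and the only general event capture scheduled before the window closes at Day 34 to Day 42 applies criteria without a grade. Grade 3-4 laboratory values meeting none of the four criteria are not counted, and the Grade 4 backstop does not help at Grade 3.

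The size of the loss is unknown. The 12 of 14 entries in Table 1-2 show that the affected category is large, not what fraction would go missing. The conclusion assumes that AE reports feed the table and that the Day 56 form does not look back to collect laboratory grades. The documents state neither, but the schedule points that way.

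The consequence is confined to a secondary safety endpoint. The primary endpoint, the sample size and the monitoring of Day 30 mortality and capillary leak syndrome are unaffected. This is a cheap improvement to make before analysis, not a flaw in the trial's main conclusion.

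**What to change.** In section 5.4.11, keep the AE-based table, name its source, and add a laboratory-graded tabulation:

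- Grade platelets, neutrophils and albumin under CTCAE v5 from the recorded values between first infusion and 28 days after the last dose, whatever their AE status.
- Show each patient's worst grade against the last grade before first infusion, so that a low starting value is not counted as new toxicity.
- Report bilirubin in a separate table, labelled as also being the liver aGVHD staging variable.
- Grade CK only where it was measured, with the number measured shown.

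Add a matching sentence to section 3.4.2.9. Leave section 4.4.1 unchanged for AE and SAE reporting.

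The cost is a few sentences and some programming, with no new visits or samples. This assumes that the required results are held as numeric values in the study database, which the protocol does not state. There are two downsides. The reported Grade 3-4 frequency will be higher. Coverage is also limited to scheduled draws: for platelets, neutrophils and albumin these are infusion days and Day 28, with nothing scheduled for the 28 − 6 = 22 days between a Day 6 last dose and Day 28; bilirubin is weekly. The new table therefore supplements the AE table and does not replace it.
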